Surgical decision making regarding concomitant management of pelvic organ prolapse (POP) and symptomatic or “occult” stress urinary incontinence (SUI) is complex and controversial.¹ One in five women will undergo prolapse surgery in their lifetime, and there is a strong correlation between prolapse and urinary incontinence.^{2,3}

Pelvic floor surgeons aspire to improve relevant quality of life outcomes for women with pelvic floor disorders while minimizing complications and unnecessary procedures. Consider the patient who has POP and SUI who undergoes an extensive vaginal repair and synthetic sling and then suffers from prolonged urinary retention post-operatively without a clear answer as to the etiology. Similarly, we have also experienced disappointment and frustration when a patient returns following POP repair with new symptoms of SUI that she ranks as a greater disruption to her quality of life than her original vaginal bulge. Another potential troublesome scenario is a significant surgical complication such as post-operative pain or voiding dysfunction that occurs during the placement of a “prophylactic” sling for “occult” SUI.

Efficacy and risk always compete for equilibrium. Level I evidence has demonstrated a positive efficacy benefit of a concomitant synthetic mid-urethral sling in women with⁴, and without⁵, pre-operative symptoms of SUI who are undergoing POP repair. Surgical correction of prolapse, with elevation of the vaginal apex and straightening of the angle between the bladder base and the urethra, has the potential to increase existing, or unmask “occult” SUI symptoms.⁶

Concomitant sling placement has been shown to reduce the risk of de novo or persistent SUI from 50% to 23%.⁵ The combination of surgical treatment of POP and SUI at the same time, however, increases the risk of incomplete bladder emptying.⁵ There is a delicate balance between placing a sling that is tight enough to prevent SUI but loose enough to allow normal voiding function. This is the primary justification of surgeons who employ a staged approach and elect only to treat those who develop bothersome SUI postoperatively.

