To conduct a multi-center, prospective, randomized, single-blind trial of retropubic (RP) versus single-incision sling (SIS) in women with \geq Stage II pelvic organ prolapse and objectively confirmed stress urinary incontinence who are undergoing native tissue vaginal repair.

The **primary outcome** will be **abnormal lower urinary tract function**, a composite outcome defined as the presence of any the following at 1 year post-surgery: subjective stress incontinence symptoms or retreatment for persistent / de novo stress urinary incontinence or retreatment for urinary retention. This study is a non-inferiority study design.

Hypothesis 2: SIS is associated with fewer intra-and post-operative complications up to 1 year following surgery due to fewer sling related complications including urinary tract injury; bleeding; de novo or worsening urge incontinence symptoms; urinary tract infection, mesh exposure, need for prolonged catheter drainage and reoperations than RP slings.

Specific Aim 2:

To compare intra- and post-operative sling related complications, de novo or worsening urge incontinence symptoms and need for prolonged bladder drainage up to 1 year post-operatively in women randomized to RP versus SIS sling at the time of native tissue vaginal repair.

SUBJECT SELECTION

Inclusion Criteria

1. At least 21 years of age
2. Women being considered for a native tissue vaginal repair in any vaginal compartment or colpocleisis
3. POP \geq stage II of any vaginal compartment, according to the pelvic organ prolapse quantification (POP-Q) system [31]
4. Vaginal bulge symptoms as indicated by an affirmative response to question 3 of the PFDI-SF20 with some degree of bother (answer must be somewhat, moderately, or quite a bit): Do you usually have a bulge or something falling out that you can see or feel in the vaginal area?
5. Positive standardized cough stress test on clinical examination, or on urodynamic testing
6. Understanding and acceptance of the need to return for all scheduled follow-up visits and willing to complete study questionnaires
7. Able to give informed consent

Exclusion Criteria

1. Prior surgery for stress urinary incontinence including mid-urethral sling; Burch/MMK; fascial pubovaginal sling (autologous, xenograft or allograft; urethral bulking injection)
2. Status post reconstructive pelvic surgery with transvaginal mesh kits or sacrocolpopexy with synthetic mesh for prolapse

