All surgeons will watch a standardized video regarding SIS sling placement prior to study launch. A 1.5 cm incision will be made at the level of the mid-urethra. The sling/needle assembly is advanced behind the ischiopubic rami in a transobturator trajectory toward the obturator space bilaterally. The needle is then removed by simply sliding the fixating tip back out. The other side is then completed in an identical fashion. The sling will be tensioned so that it will lie in direct apposition to the urethra but will still permit passage of an instrument between the mesh and the urethra. The adjustment thread is then cut short and the vaginal incision is closed with an absorbable suture.

Following SIS placement, **2 small superficial skin incisions will be made in the same location as the exit sites of a RP sling.** Dermabond or steri strips will be applied.

Any intra-operative adverse events will be recorded on data collection forms.

Post-operative care and procedures for voiding trials will not be standardized. Day of discharge and method of voiding (spontaneous, self-catheterization, suprapubic catheter, or indwelling foley) will be recorded.

POST-INTERVENTION ASSESSMENTS:

The primary study endpoints will be assessed at 6 weeks and 12 months after the index surgery via a clinic visit and health-related quality of life interview/completion of questionnaires. Individual site study coordinators will collect follow-up healthcare utilization data and update the medical history at 6 and 12 months. Study coordinators will complete a telephone interview at 6 months to assess for any Adverse Events.

Clinical outcomes

This trial has a composite **primary** dichotomous outcome of **abnormal lower urinary tract function** at 12 months post-operatively (YES or NO) that is defined as ANY of the following:

1. Subjectively bothersome stress incontinence symptoms at 12 months post-operatively, as measured by a positive response of > 1 to Question 17 on PFDI-20.
2. Any retreatment for stress incontinence including pelvic floor physical therapy; incontinence pessary; urethral bulking injection; repeat incontinence surgery
3. Surgical intervention for urinary retention (sling lysis or revision) at any time point post-operatively

Secondary outcome measures will assess the degree to which the study intervention influences adverse events intra- and post-operatively and will include the following:

1. Adverse events

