2. De novo (new affirmative response of > 1 to Question 16 on PFDI-20) or worsening urge incontinence symptoms (increase of score on Question 16 by 2 points or more on PFDI-20) at 12 months post-operatively.
3. Surgeon satisfaction with the sling will be assessed immediately post-operatively with a 10-point VAS.
4. Patient Global Impression of Improvement (PGI-I) Scale for incontinence symptoms.²⁶
5. Need for bladder drainage beyond 6 weeks post-operatively

POWER CALCULATION:

This study is a non-inferiority study design. The null hypothesis is that the difference in the proportion of women with abnormal bladder function in the SIS group compared to RP sling group is 12% or more (noninferiority margin: H0: RP-SIS_ 0.12). Based on criteria used in a previously published multicenter trial of mid-urethral slings, we chose a noninferiority margin of 12%. Assuming a subjective cure rate for RP of 82%, 127 individuals in each group will provide 80% to reject the null hypothesis (H0) that the true difference in cure rates between the two procedures (% cure RP and % cure ALTIS SIS sling) is less than or equal to 12% in favor of the alternate hypothesis (H1: SIS-RP_ 0.12) that the true difference

in proportions is greater than 12% using a two-group large-sample normal approximation test of proportions with a one-sided 5% significance level. Assuming a 10% loss to follow-up or drop-out rate for the duration of the study, the total enrollment goal is 280. Non-inferiority was declared if the upper bound of the 95% confidence interval for the between group difference in bladder function was less than 12%. To minimize bias toward non-inferiority, only women treated per protocol (ie: underwent the randomized sling) were considered in the primary outcome analysis. A secondary analysis of the primary outcome was performed on the intent to treat population. Likewise, other secondary outcome measures were performed on the intent to treat population.

CALENDAR OF EVENTS

| | Baseline | Surgery | Day of DC | 2 weeks | 6 weeks | 6 months | 12 months |
|-------------------------------------|----------|---------|-----------|---------|---------|----------|-----------|
| Informed Consent | X | | | | | | |
| CRF | X | X | X | X | X | | X |
| Demographic information | X | | | | | | |
| Charlson Comorbidity Index | X | | | | | | |
| POP-Q | X | | | | X | | X |
| PFDI-20 short form | X | | | | X | | X |
| PFIQ -7 short form | X | | | | | | X |
| PISQ-IR | X | | | | | | X |

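### The 127 per arm and 80% power are calculated for an undefined 82% subjective cure rate, while the primary test is on the composite of abnormal lower urinary tract function, for which the protocol states no rate

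*Protocol*

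**What the plan says.** The POWER CALCULATION section of the protocol describes one primary non-inferiority test in four statements.

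- **First null.** It concerns the composite: "the difference in the proportion of women with abnormal bladder function in the SIS group compared to RP sling group is 12% or more".
- **Sizing assumption.** It concerns cure: "Assuming a subjective cure rate for RP of 82%, 127 individuals in each group will provide 80% to reject the null hypothesis (H0").
- **Second null.** It also concerns cure, and refers to the difference between % "cure RP and % cure ALTIS SIS sling) is less than or equal to 12% in favor of the alternate hypothesis" that this difference exceeds 12%. The level is that of a "normal approximation test of proportions with a one-sided 5% significance level".
- **Decision rule.** It returns to bladder function: "Non-inferiority was declared if the upper bound of the 95% confidence interval for the between group difference in bladder function was less than 12" per cent.

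The primary outcome is defined in two other places. Specific Aim 1 calls it "a composite outcome defined as the presence of any the following at 1 year post-surgery". The Clinical outcomes part of POST-INTERVENTION ASSESSMENTS lists three components, any one of which counts as failure: bothersome stress incontinence on PFDI-20 Question 17 at 12 months, any retreatment for stress incontinence, and "Surgical intervention for urinary retention (sling lysis or revision) at any time point post-operatively".

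The protocol does not define subjective cure, give the SIS rate used for sizing, or give a composite rate for either arm.

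**The concern.** With a fixed absolute margin, power depends on the event rates of the endpoint that is tested and on the confidence level of the decision rule. Here the rate belongs to a quantity called subjective cure, while the test is on a three-part composite. Retreatment and retention surgery can add failures to the composite that a symptom-only definition of cure would not count. A reader therefore cannot confirm that the stated 80% belongs to the primary test.

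Two further statements in the section add to the difficulty.

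- The second null, read literally, would have the trial reject a difference of at most 12 points in favour of a larger one. That is the reverse of a non-inferiority conclusion.
- The sample size uses one-sided 5%, but the decision rule uses a 95% interval without saying whether it is one-sided or two-sided.

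**Working it through.** **Inputs (POWER CALCULATION).** RP subjective cure 82%, margin 0.12, one-sided 5%, power 80%, 127 per arm. The SIS rate is not stated and is taken as equal to RP.

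**1. Reproduce the stated sample size.** With failure rate p = 1 − 0.82 = 0.18 in both arms and a true difference of zero:

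n = (z_α + z_β)² × 2p(1 − p) / margin²

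n = (1.645 + 0.8416)² × (2 × 0.18 × 0.82) / 0.12² = 126.7, so 127 per arm.

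The figure is right for these inputs.

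**2. Power at 127 per arm for equal composite rates.**

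Power = Φ( 0.12 / √(2p(1 − p)/127) − z )

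At p = 0.18 the standard error is √(0.2952/127) = 0.0482 and 0.12/0.0482 = 2.489.

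- One-sided 5%: Φ(2.489 − 1.645) = 80.1%.
- One-sided 2.5% (two-sided 95% interval): Φ(2.489 − 1.960) = 70.2%.

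The protocol gives no composite rate, so every rate below is an assumption.

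| Composite rate, both arms | Power, one-sided 5% | Power, one-sided 2.5% |
|---|---|---|
| 15% | 84.9% | 76.4% |
| 18% | 80.1% | 70.2% |
| 20% | 77.2% | 66.7% |
| 23% | 73.5% | 62.3% |
| 25% | 71.3% | 59.8% |

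With equal rates and one-sided 5%, 127 per arm gives 80% only if the composite rate is no more than about 18.0%.

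**3. What 82% could mean.**

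- *Freedom from the composite.* The composite rate is then 18%. If the same rate is assumed for SIS, 127 per arm stands at one-sided 5%.
- *Absence of subjective stress incontinence only, as in component 1.* The composite rate is at least 18%, since components 2 and 3 can only add failures. With equal rates, power is at most 80.1%.
- *Some other measure of cure.* The composite rate could lie on either side of 18%.

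**4. Direction of the two nulls.** Let p be the failure proportion and c = 1 − p. Then c_RP − c_SIS = p_SIS − p_RP.

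- The first null, p_SIS − p_RP ≥ 0.12, is a proper non-inferiority null.
- The second null, as worded, puts a cure difference of at most 12 points in the null and a larger one in the alternative. If the difference is RP minus SIS, rejecting it shows SIS worse by more than the margin. If it is SIS minus RP, rejecting it shows SIS better by more than 12 points. Neither is non-inferiority.
- With minus signs, c_SIS − c_RP ≤ −0.12 against > −0.12, the second pair would agree with the first.

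**The case against.** The strongest reply is that this is a gap in wording and that nothing has been shown to be underpowered. Several parts of that reply stand.

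- The cure sentence sits inside a single calculation, between two statements on bladder function and with the same 12-point margin. Differences in cure and in failure mirror each other, and 127 reproduces exactly at 18% failure in both arms. Reading 82% as freedom from the composite is natural. The protocol does not state it, however, and the word subjective points equally well to component 1 alone.
- The missing SIS rate matters little, because equal rates are the usual assumption and they reproduce 127.
- The reversed second null may be an artefact. Both formulas have lost a symbol in the available text, and missing minus signs would explain the wording. The decision rule is clear on endpoint and direction, so it cannot fairly be said that the trial does not know what it will test.
- The confidence-level question is separate from cure versus composite. The 70.2% should not be counted as a result of the endpoint mismatch.

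A reader might infer a real shortfall from the background statement "Concomitant sling placement has been shown to reduce the risk of de novo or persistent SUI from 50% to 23" per cent, since 23% in both arms gives 73.5%. The documents do not support that inference. The figure is for stress incontinence only, not the composite, and the background attaches its source to women without pre-operative symptoms, whereas this trial enrols symptomatic and occult cases. The Altis cure rates of 84% and 81% come from non-comparative studies, the second at 24 months, and are not composite rates either.

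**Conclusion.** The point holds as a defect in how the sample size is tied to the primary test. The stated 80% is calculated for an undefined cure rate, the test is on the composite, and the protocol does not link the two. With equal rates, the 80% carries over to the composite only if the composite rate is at most about 18% in both arms and the decision bound is one-sided 5%.

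A reader might go further and conclude that the trial is underpowered for its primary outcome, or that 127 is wrong. The protocol supports neither: the arithmetic is correct for its inputs, and if 82% means freedom from the composite, 127 stands at one-sided 5%. If 82% covers component 1 only, equal-rate power is at most 80.1%, falling to 77.2%, 73.5% and 71.3% at assumed rates of 20%, 23% and 25%.

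The separate question of sidedness has a definite size under the protocol's own inputs. If the 95% interval is two-sided, power at 18% in both arms is 70.2%, which is 9.9 percentage points below the 80.1% obtained at one-sided 5%. The protocol should be corrected, but nothing here invalidates the design.

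**What to change.** In POWER CALCULATION:

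1. Replace both nulls with one pair on the composite: H0: p_SIS − p_RP ≥ 0.12; H1: p_SIS − p_RP < 0.12, where p is the proportion with abnormal lower urinary tract function at 12 months (any of components 1 to 3).
2. State that 82% is freedom from the composite, so that 18% abnormal is assumed in both arms. If that was not the intention, give the assumed composite rate for each arm.
3. State the confidence level and sidedness of the interval so that it matches the sizing alpha, and restate power at 127 per arm for that rate and level. At 18% in both arms it is 80.1% with a one-sided 95% bound (equivalently a two-sided 90% interval), and 70.2% with a two-sided 95% interval.

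This changes protocol wording only, with no added enrolment or data collection. The cost is that the printed power may be less favourable than 80%.

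### The power sentence states the non-inferiority hypotheses in the wrong direction, and the sizing test and the 95% interval rule are not tied to the same error level

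*Protocol*

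**What the plan says.** All the statements at issue stand in one paragraph of the Protocol, under POWER CALCULATION.

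- **Opening null.** The difference in the proportion with "abnormal bladder function in the SIS group compared to RP sling group is 12% or more".
- **Power sentence.** It begins "Assuming a subjective cure rate for RP of 82" percent and continues that "127 individuals in each group will provide 80% to reject the null hypothesis (H0"). That null is that the true difference in cure rates "is less than or equal to 12% in favor of the alternate hypothesis". The alternative is that the true difference "in proportions is greater than 12% using a two-group large-sample normal approximation test of proportions".
- **Level of the sizing test.** "normal approximation test of proportions with a one-sided 5% significance level".
- **Decision rule.** Non-inferiority is declared on the "upper bound of the 95% confidence interval for the between group difference in bladder function was less than 12" percent.

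The paragraph also gives the hypotheses in symbols, with H0 written on RP minus SIS and H1 on SIS minus RP. In the text available here the inequality operators in both are lost, so nothing below relies on them.

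Under Clinical outcomes, the primary outcome is a composite. It counts bothersome stress incontinence symptoms, any retreatment for stress incontinence, and "Surgical intervention for urinary retention (sling lysis or revision) at any time point post-operatively".

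**The concern.** In a non-inferiority test the null is that the new treatment is worse by the margin or more, and rejecting it shows that any deficit is smaller than the margin. The opening null and the decision rule follow this pattern: a difference under 12 points is what must be shown. The power sentence, placed between them, makes a difference of 12 points or less the null and a larger difference the alternative.

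Neither order of subtraction rescues those words. If the difference is RP minus SIS in cure, rejection would show SIS to be worse by more than the margin. If it is SIS minus RP, rejection would show SIS to be better by more than 12 points, which against 82% means cure above 94%. Neither is non-inferiority. The 80% power is therefore attached to a null that it does not fit.

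A second mismatch lies in the same lines. The trial is sized with a one-sided 5% test, but the claim is decided on a 95% confidence interval whose sidedness is not given. If the interval is two-sided, the claim is judged at one-sided 2.5%, and the stated power no longer describes the rule that will be applied.

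**Working it through.** **Inputs.** From POWER CALCULATION: RP cure 82%, margin 0.12, 127 per arm, power 80%, one-sided 5%, large-sample normal test. SIS cure is not stated. I assume 82% there too (true difference zero), because this reproduces the stated number.

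**1. Reproduce 127 with the correctly directed test.**
n = (z_0.95 + z_0.80)² × 2 × 0.82 × 0.18 / 0.12²
= (1.6449 + 0.8416)² × 0.2952 / 0.0144
= 6.1827 × 20.5 = 126.74, so 127 per arm.

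**2. Power at 127 per arm.**
SE = √(0.2952 / 127) = 0.04821, and 0.12 / 0.04821 = 2.489.
Power = Φ(2.489 − 1.645) = Φ(0.844) = 0.801.
This applies equally to H0: SIS − RP ≥ 0.12 on the failure scale and to H0: SIS − RP ≤ −0.12 on the cure scale, since they are the same test.

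**3. The sentence as printed, same inputs.** Rejecting a difference of 12 points or less in favour of a larger one, when the true difference is zero, has probability
Φ(−2.489 − 1.645) = Φ(−4.134), about 0.00002.

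Under other SIS cure rates, with RP at 82% and 127 per arm:

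| Order of subtraction (cure) | SIS cure | Chance of rejecting the printed H0 |
|---|---|---|
| SIS − RP | 94% | 5% |
| SIS − RP | 98% | 29% |
| SIS − RP | 100% | 55% |
| RP − SIS | 60% | 57% |
| RP − SIS | 55% | 85% |

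On the first order, 80% cannot be reached. On the second, it needs SIS cure between 55% and 60%, which no one would plan for.

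**4. Do other tests give 127?** A superiority comparison of 82% with 70% needs 156 (one-sided 5%) or 198 (two-sided 5%) per arm. One of 82% with 94% needs 90 or 114. Of the tests tried, only the conventional non-inferiority test at one-sided 5% returns 127.

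**5. The interval level.** A one-sided 95% bound, which is the upper limit of a two-sided 90% interval, is the test in step 2, with power 80.1%. If the 95% interval is two-sided, its upper limit uses 1.960:
Power at 127 = Φ(2.489 − 1.960) = Φ(0.529) = 0.702.
n for 80% = (1.9600 + 0.8416)² × 20.5 = 7.849 × 20.5 = 160.9, so 161 per arm.

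**The case against.** The strongest reply is that the intent is plain. The opening null names SIS compared to RP and points the right way. The decision rule agrees with it, and with an upper bound below 12% only SIS minus RP in abnormal function makes sense. Hypothesis 1 says non-inferior. An analyst reading the whole section would run the right test. All of this stands, and it is why the direction error is minor. A reader might infer that the trial would be analysed in the wrong direction, or that the sample size is wrong. The documents support neither: step 1 shows that 127 came from the proper test.

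A reader might also infer that a minus sign was dropped. The words would indeed fit a cure-scale pair at minus 12%, but swapped inequalities on RP minus SIS fit equally well. The symbolic hypotheses could be sound in the original, since only their operators are missing here. A sign lost when the text was read cannot be fully excluded, although it would have to be lost in both verbal statements. The cause cannot be settled, and the correction does not depend on it.

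It can be said, too, that the interval level is a different matter from the direction and is conditional. That is fair. The Protocol does not say the interval is two-sided, so it would be too strong to call the trial underpowered. What stands is that the stated 80% holds on one reading and not on the more usual one, and the section does not say which applies.

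**Conclusion.** The point holds as a minor error of statement. The power sentence words the hypotheses in the direction opposite to the section's own null and decision rule. Putting this right changes neither the 127 per arm nor the 12% margin.

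The consequence with a number attached is the unstated sidedness: power is 80.1% with a one-sided 95% bound and about 70% with a two-sided 95% interval.

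These figures rest on 82% cure in both arms, the normal approximation, and 127 evaluable women per arm. They also treat 18% failure as a stand-in for the composite. The composite adds retreatment and surgery for retention to symptoms, and the Protocol gives no planning rate for it. The sample size is therefore confirmed on the subjective-cure scale, not independently for the composite.

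**What to change.** 1. **Hypotheses.** State one pair and delete the others: H0: p_SIS − p_RP ≥ 0.12 versus H1: p_SIS − p_RP < 0.12, where p is the proportion with abnormal lower urinary tract function at 12 months.
2. **Decision rule.** Declare non-inferiority if the upper confidence bound for p_SIS − p_RP is below 0.12.
3. **Planning value.** Say that the power figure assumes 82% subjective cure in both arms, used as a stand-in (18% failure) for the composite, which has further components.
4. **Level.** Choose one. Either specify a one-sided 95% bound (two-sided 90% interval), which matches the one-sided 5% test and the stated 80%, or keep a two-sided 95% interval and restate the power as about 70% at 127 per arm.

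The cost is a few sentences. Items 1 to 3 leave sample size and margin as they are, and neither option in item 4 adds enrolment. Only holding 80% power with a two-sided 95% interval would do so: 161 evaluable women per arm, which is 161 − 127 = 34 more in each.

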3. Any serious disease, or chronic condition, that could interfere with the study compliance
4. Unwilling to have a synthetic sling
5. Inability to give informed consent
6. Pregnancy or planning pregnancy in the first postoperative year
7. Untreated urinary tract infection (may be included after resolution)
8. Poorly-controlled diabetes mellitus (HgbA1c > 9 within 3 months of surgery date)
9. Prior pelvic radiation
10. Incarcerated
11. Neurogenic bladder/ pre-operative self-catheterization
12. Elevated post-void residual (>150 ml) that does not resolve with prolapse reduction testing (pessary, prolapse reduced uroflow or micturition study)
13. Prior augmented (synthetic mesh, autologous graft, xenograft, allograft) prolapse repair
14. Planned concomitant bowel related surgery including sphincteroplasty and perineal rectal prolapse surgery, rectovaginal fistula repair, hemorrhoidectomy.

STUDY POPULATION, RECRUITMENT AND SCREENING

Study population participants will consist of women having native tissue vaginal repair in any vaginal compartment. Participants must have vaginal bulge symptoms defined by positive responses to a validated instrument, the Pelvic Floor Distress Inventory²³ and Stage II or greater POP in any vaginal compartment as determined by the Pelvic Organ Prolapse Quantification (POPQ) system²⁴, a validated tool designed to assess the degree of vaginal prolapse. Participants must have objective evidence of stress incontinence on physical examination, with or without prolapse reduction, or on urodynamic testing. Women will be grouped according to whether they have SYMPTOMATIC or OCCULT SUI for randomization purposes.

Study subjects will be recruited from patients who present to the urogynecology clinical sites at Wake Forest Baptist Health, the Women's Health Institute at the Cleveland Clinic, Northwestern, MedStar Washington Hospital Center, Women's and Infants' Hospital of Rhode Island, Atrium Health, and Groote Schuur Hospital at the University of Cape Town, and the private practice clinic of [name]. Wake Forest Baptist Health will serve as the central Data Coordinating Center. Institutional review board (IRB) approval will be obtained at each participating site.

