Potential subjects will be identified by members of the sections of Urogynecology and Reconstructive Pelvic Surgery and Benign Gynecology at the respective institutions. Eligible patients who agree to participate will be provided written informed consent administered by the collaborators listed on each Institutional IRB document.

PRE-INTERVENTION ASSESSMENTS:

All women presenting to the participating clinical centers with signs and symptoms of prolapse and objective stress incontinence (symptomatic or occult) will be screened for their eligibility. If eligible and consenting, the following baseline data will be collected on paper forms that will then be transcribed into a secure RedCap database:

1. Demographic data including age, race, BMI, insurance status
2. Health-related quality of life (SF-12), and measurement of Charlson Comorbidity Index
3. Smoking status (Yes or No)
4. POP-Q data
5. Presence of vaginal atrophy (Yes or No)
6. Menopausal status, including current exposure to topical vaginal estrogen, parity, and urogynecologic surgeries
7. Current exposure to anticholinergic medication (Yes or No)
8. Objective assessment of stress incontinence: Clinical or urodynamic assessment is permitted.
 - a. **Clinical cough stress test:** Participants that have no prior objective SUI will be instructed to present with a full bladder . If empty, the bladder can be retrograde filled with 300 ml. In the lithotomy position, subjects will be asked to **cough and strain (Valsalva) while the urethral meatus is observed and the POP is reduced.** If no leakage is demonstrated, the reduction cough stress test will be repeated in the standing position. **Women will be categorized as having symptomatic vs occult SUI for sub-analysis and block randomization.**
 - b. **Urodynamic testing:** Participants may undergo standard urodynamic testing with prolapse reduction. A cough stress test at bladder capacity will be performed. If no leakage is demonstrated at capacity with the catheters in place, the catheters will be removed and the cough stress test repeated. Valsalva leak point pressures will be recorded.
9. Assessment of post-void residual volume (collected via bladder scan or CIC)
10. A series of instruments will be used to measure symptom bother: the Pelvic Floor Distress Inventory short form-20,²³ Pelvic Organ Prolapse/Urinary Incontinence Sexual Functioning Questionnaire Short Form (PISQ-IR)²⁵ and PFIQ-7.

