NOTE: Standard of care assessments (POP-Q, UDS, PVRs) are valid to use for the study if they were performed within 6 months of the subject signing consent. Also, if any standard of care questionnaires (matching the study questionnaires) were administered within 6 months before signing consent, they may also be used

in the place of baseline questionnaires and not repeated. Dates of assessments just need to be clear if they were not performed the same day as baseline. Also, make sure all assessments required for the study have been performed per baseline visit requirements.

RANDOMIZATION AND MASKING:

A computer-generated random allocation using a randomly permuted block design (10 subjects per block) will be stratified by clinical site and presence of symptomatic versus occult SUI. Randomization will be assigned in the operating room to minimize surgeon and participant bias. While it is impossible for surgeons to be masked to the randomization, participants will be masked during the one-year follow-up period. Dictated operative notes will list the type of sling under procedures as “per study protocol” and then describe the type of sling used within the body of the operative note. Precautions will be taken to minimize unmasking the study groups: Since RP slings require two suprapubic stab incisions, identical sham incision will also be performed in the SIS group. Surgical wound dressings will be identical for all participants. Finally, all participants, regardless of randomization, will have postoperative indwelling urethral catheters until voiding trials are performed.

STUDY INTERVENTION:

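### Does stratified randomisation make the unstratified two-group test in the power calculation an error in the plan?

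*Protocol*

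**What the plan says.** Under Randomization and Masking, the protocol uses a "randomly permuted block design (10 subjects per block") and says that the allocation "will be stratified by clinical site and presence of symptomatic versus occult SUI". Two other sections give the SUI category a purpose. Study Population, Recruitment and Screening says: "Women will be grouped according to whether they have SYMPTOMATIC or OCCULT SUI for randomization purposes". The clinical cough stress test item under Pre-intervention Assessments says: "Women will be categorized as having symptomatic vs occult SUI for sub-analysis and block randomization".

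The Power Calculation section does two separate things.

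- **Sizing.** It states: "Assuming a subjective cure rate for RP of 82%, 127 individuals in each group will provide 80" per cent power against a 12% margin. The method given for that figure is "using a two-group large-sample normal approximation test of proportions with a one-sided 5% significance level".
- **Decision rule.** Later in the same paragraph it states: "Non-inferiority was declared if the upper bound of the 95% confidence interval for the between group difference in bladder function was less than 12" per cent. No interval method, covariate or stratum is named there.

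**The concern.** An analysis should normally reflect the factors used to restrict the randomisation. Stratified allocation balances the arms on those factors, so the true variance of the treatment difference falls when they are prognostic. An analysis that ignores them estimates the variance as if that balance did not exist, and its interval is then too wide.

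SUI type could well be prognostic here. The composite primary outcome includes bothersome stress incontinence at 12 months and retreatment for it, and symptomatic or occult SUI is the baseline form of the same complaint. Yet the protocol gives SUI type a role only in randomisation and sub-analysis, and the one test it names has no strata. Since non-inferiority turns on a single confidence limit, a limit wider than necessary could cost the trial a conclusion that its data support.

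**Working it through.** **Inputs.** From the Power Calculation section: retropubic cure 82%, so failure 18%; margin 0.12; one-sided 5%; 127 per group. Assumed, because the protocol does not give them: no true difference between slings, two equal SUI strata, and failure rates by SUI type that average 18%.

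**Step 1: the plan's own figure.** With the unstratified normal approximation,

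n = (1.645 + 0.842)² × 2 × 0.18 × 0.82 / 0.12² = 126.8, rounded up to 127.

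The standard error at 127 per arm is √(2 × 0.1476 / 127) = 0.0482, and power is Φ(0.12/0.0482 − 1.645) = 80.1%. The named test therefore does its job in the sentence where it stands.

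**Step 2: what ignoring SUI type would cost.** With failure rates a and b in the two strata:

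- V = 0.5·a(1 − a) + 0.5·b(1 − b), and the true SE under stratified allocation is √(2V/127).
- The unstratified analysis still uses SE = √(2 × 0.1476/127) = 0.04821.
- Unstratified power = Φ((0.12 − 1.645 × 0.04821) / true SE).
- Stratified power = Φ(0.12 / true SE − 1.645).

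| Failure by SUI type | V | True SE | Half-width at 1.96, stratified (points) | Power, unstratified | Power, stratified |
|---|---|---|---|---|---|
| 18% / 18% | 0.1476 | 0.04821 | 9.45 | 80.1% | 80.1% |
| 22% / 14% | 0.1460 | 0.04795 | 9.40 | 80.2% | 80.4% |
| 26% / 10% | 0.1412 | 0.04716 | 9.24 | 80.6% | 81.6% |
| 28% / 8% | 0.1376 | 0.04655 | 9.12 | 80.9% | 82.5% |

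The unstratified half-width is 9.45 points in every row, so it is at most 9.45 − 9.12 = 0.33 points too wide. Unstratified power never falls below the planned value, because stratified allocation also helps the unstratified test. If the 95% interval is two-sided (one-sided 2.5%), the largest gain is 2.4 points (70.8% to 73.2%). Whether the interval is one-sided or two-sided is a separate question.

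**Step 3: error rate.** In 400,000 simulated trials per scenario at a true 12-point difference and one-sided 5%, the unstratified type I error was 5.0%, 5.0%, 4.8% and 4.6% in the order of the table. For a Mantel-Haenszel interval stratified on SUI type it was 5.0%, 5.1%, 5.1% and 5.1%. The unstratified analysis errs on the safe side.

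**Step 4: using the strata actually randomised on.** Eight sites by two SUI types make 16 cells, about 280/16 = 17.5 women each. With equal site sizes assumed, an analysis over all 16 cells changed simulated power against the unstratified test by −0.4, −0.2, +0.6 and +1.3 points. Full stratification is thus no automatic improvement.

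**The case for a change.** The strongest case for the concern is that the protocol is not simply silent. It names an unstratified test beside a stratified design and gives SUI type only other uses. A reader could take the sizing test as the intended analysis. A prognostic effect of SUI type is plausible, the factor is already recorded, and stratifying on it alone loses essentially nothing if it proves unrelated to outcome. Settling the interval method in advance would also remove a choice between two limits that could fall on opposite sides of 12%.

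Parts of this stand. Stratifying on SUI type is a reasonable choice, and the method should be settled before the arms are compared. But a test named to justify a sample size does not bind the analysis, and sizing without strata is compatible with stratified allocation. The protocol nowhere says that the strata will be ignored. Step 4 also shows that the choice of strata takes judgement: the option that gains most uses SUI type and leaves out site, although both were randomised on. That decision commonly belongs in the statistical analysis plan, and its absence from a protocol is not a fault.

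**Conclusion.** The concern does not hold. The unstratified test is stated correctly for its purpose and reproduces 127 per group. The decision rule neither requires nor excludes a stratified interval, so nothing in the protocol contradicts the stratified randomisation.

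An unstratified interval would still support a sound conclusion: type I error at or below nominal, apart from simulation error, and power at or above the planned 80%. What stratifying on SUI type could add is 0 to 1.6 power points at one-sided 5%. The upper end needs failure of 28% in one stratum and 8% in the other, a 3.5-fold ratio for which the protocol gives no support. These sizes rest on the assumed stratum rates, equal strata, no true difference, and balance within SUI strata surviving incomplete blocks and per-protocol exclusions. What remains is an efficiency preference for the analysis plan, with no correction due in the protocol.
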